6.1.8. Actual Treatment

Safety data will be summarized by the actual treatment group. In case of study intervention dispensing error (eg, dispensing wrong kit), participants might receive a treatment other than the dose level they were randomized to receive. If dispensing error happens rarely, the participant

will remain in the original assigned treatment group, but a footnote should be added to describe the affected data point due to the dispensing error. If the dispensing error is recurrent and participant takes > 50% of the error treatment group over the study period, the participant should switch to the majority treatment group.

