4. ANALYSIS SETS

| Analysis Set | Description |
|---------------------------------|---|
| Randomized Set | All randomized participants grouped by randomized treatment group. |
| Re-randomized Set | All re-randomized placebo arm (Group 3) participants grouped by re- randomized treatment group. |
| Full Analysis Set (FAS) | All randomized participants who received at least 1 dose of the study intervention and have a baseline and at least 1 postbaseline efficacy assessment. Participants will be analyzed as randomized. |
| PK Analysis Set | All randomized participants who have a baseline PK assessment and at least 1 evaluable postdose PK assessment. |
| PD Analysis Set | All randomized participants who have a baseline PD assessment and at least 1 evaluable postdose PD assessment. |
| Per Protocol Set (PPS) | All participants in the FAS without important protocol deviations. See Section 6.2.2 for the list of important protocol deviations. |
| Safety Set (SS) | All randomized participants who received at least 1 dose of the study intervention. Participants will be analyzed according to the study intervention they actually received. (Study intervention received is the same as planned study intervention if the participant has received at least 1 dose of planned study intervention. If planned study intervention is not received at all, the most frequently received study intervention will be the received study intervention). |
| ALXN2050-Treated Set | All randomized participants who received at least 1 dose of the ALXN2050. Participants will be analyzed according to the study intervention they actually received. (Study intervention received is the same as planned study intervention if the participant has received at least 1 dose of planned study intervention. If planned study intervention is not received at all, the most frequently received study intervention will be the received study intervention). |
| Open-label Extension Set (OLES) | All randomized participants who received at least 1 dose of ALXN2050 during the OLE Period. |

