5.6.1. Safety Analyses at Analysis 1 (Week 8)

All outputs for safety outcomes of the Primary Treatment Period (first 8 weeks) will be based on the SS, unless otherwise specified. All safety analyses for participants during the ALXN2050 treatment period will be based on the ALXN2050-Treated Set. Safety data will be summarized

by the actual treatment received (Groups 1, 2, 3, 3a, and 3b, as applicable). Baseline is defined as the last available assessment prior to the first dose of study intervention.

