5.6.2.2. Adverse Events

AEs during the respective period for each group will be analyzed and reported in terms of TEAEs, which are defined as follows:

• Groups 3a and 3b: any AEs that started or worsened in severity on or after the first dose of study intervention in the ETP and before the first dose in the OLE Period or, if discontinued before the OLE Period, before the last dose + 30 days. The same analyses as specified in Section 5.6.1.2 will be performed using the first 34 weeks of data (PEP and ETP) and ALXN2050-Treated Set. Additional analyses will be performed, including the aggregated PEP, ETP, and OLE Period AE data up to the cutoff date by dose received ("ALXN2050 180 mg bid" and "ALXN2050 120 mg bid") at the time of the AE using the ALXN2050-Treated Set.

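### SAP Section 4 and SAP 6.1.8 assign actual treatment by contradictory rules when a recurrent dispensing error covers more than half, but not all, of a participant's doses

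*SAP*

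**What the plan says.** SAP Section 4 defines treatment received inside the Safety Set definition and repeats the text for the ALXN2050-Treated Set: "Study intervention received is the same as planned study intervention if the participant has received at least 1 dose of planned study intervention". The alternative applies only at the extreme: "If planned study intervention is not received at all, the most frequently received study intervention will be the received study intervention".

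SAP 6.1.8 opens with "Safety data will be summarized by the actual treatment group". A participant with a rare dispensing error stays in the assigned group with a footnote. The other case is: "If the dispensing error is recurrent and participant takes > 50% of the error treatment group over the study period", then "the participant should switch to the majority treatment group".

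Both rules reach the same outputs. For the PEP, SAP 5.6.1 states: "All outputs for safety outcomes of the Primary Treatment Period (first 8 weeks) will be based on the SS, unless otherwise specified". It bases safety analyses of the ALXN2050 treatment period on the ALXN2050-Treated Set, and it groups safety data by actual treatment received without saying which rule defines that.

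Protocol 9.3 analyses the Safety Set by the intervention actually received, with no one-dose exception. SAP 6.4 records no change from the protocol. The SAP Addendum (1.2) keeps the safety analyses of SAP 5.6. It specifies exposure and adverse event summaries for the PEP by Groups 1, 2 and 3, and for the ALXN2050-treated period by Groups 1, 2, 3a and 3b. It alters neither rule.

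**The concern.** Anyone whose error share is above 50% and below 100% has, by definition, taken at least one planned dose. Section 4 then fixes that participant in the planned arm. If the error is recurrent, 6.1.8 moves the participant out. A programmer cannot follow both.

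What is at stake is which column of a by-group safety table holds the participant. Under Section 4, someone with one placebo dose and ALXN2050 for the rest of the PEP is reported as placebo, so events on active drug would count against the comparator. That is hard to square with protocol 9.3. Timing adds to the problem. Protocol 6.3.2 has selected sponsor staff unblinded from the PEP analysis onward, and the Addendum reports that the Week 8 result is already known. Choosing between two written rules now would be an unblinded decision on safety attribution.

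**Working it through.** The documents give no figure on this point to reproduce, so the check applies both rules as written to the same dosing histories.

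**Inputs.** Study drug is dispensed at weekly PEP visits, with enough to last to the next visit (protocol 4.1 and Table 2). That gives 8 dispensing intervals from Day 1 to Week 7. Dosing is twice daily. Planned enrolment is 70, randomized 2:1:2 (SAP 1.2 and Section 3).

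**Assumptions.** Full dosing; exactly 7 days per kit; one error treatment; the error counts as recurrent; and, for the table, *study period* in 6.1.8 means the PEP.

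**Doses.** 7 days × 2 = 14 per kit; 8 × 14 = 112 in the PEP.

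**Rules.** Section 4: planned arm if planned doses ≥ 1, otherwise the most frequent treatment. 6.1.8: error arm if error share > 50%, otherwise planned arm.

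| Wrong kits of 8 | Wrong doses of 112 | Error share | Section 4 | 6.1.8 |
|---|---|---|---|---|
| 0 to 4 | 0 to 56 | 0 to 50% | planned | planned |
| 5 | 70 | 62.5% | planned | error |
| 6 | 84 | 75.0% | planned | error |
| 7 | 98 | 87.5% | planned | error |
| 8 | 112 | 100% | error | error |

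Counted dose by dose, the rules disagree from 57 to 111 wrong doses. One placebo dose plus 111 ALXN2050 doses is the extreme case.

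**The other reading of *study period*.** Take a Group 3 participant given ALXN2050 in all 8 placebo weeks and treated correctly afterwards. Over the first 34 weeks the error share is 8/34 = 23.5%; over 117 weeks it is 8/117 = 6.8%. Neither exceeds 50%, so 6.1.8 does not switch the participant. No planned placebo dose was taken, so Section 4 does take the participant out of placebo. The conflict has reversed. With 5 to 7 wrong kits on this reading, both rules say placebo and the conflict in the table disappears.

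**Size.** Planned arms: 70 × 2/5 = 28 (180 mg and placebo) and 70 × 1/5 = 14 (120 mg). For an event that the participant had, 1/28 = 3.6 percentage points and 1/14 = 7.1 points. Moving the participant also takes one from one denominator and adds one to the other; for example, 28 becomes 29, and 1/29 = 3.4 points.

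**The case against.** The best case against the point is that it may affect nobody. It needs repeated wrong kits for one participant, and nothing in the documents suggests that this happened. Such a case would also be visible, because receiving the wrong randomized treatment is a listed important deviation, and all deviations and adverse events are listed. The study is a terminated proof-of-concept trial reduced to one abbreviated report. This limits the weight of the point, but listings and deviation review do not decide which column a participant occupies.

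A reader might infer more than the text supports, in four ways:

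- That one participant's events are split between arms within a table. They are not: under either rule the whole participant moves.
- That every safety table is affected. Some SAP tables use a separate attribution. Aggregated adverse events in SAP 5.6.2.2 are by dose received "at the time of the AE using the ALXN2050-Treated Set", and OLE safety data in 5.6.2.3 and 5.9 are by dose received.
- That any wrong kit triggers the conflict. 6.1.8 requires both recurrence and a share above 50%.
- That efficacy is affected. The Full Analysis Set is analysed as randomized.

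It can also be said that preferring the majority rule to the one-dose rule is a design choice. Strictly, consistency needs only one rule, a defined period and a cross-reference. That is fair, but the majority rule is closer to protocol 9.3.

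**Conclusion.** The contradiction is real. On the PEP reading, it covers every recurrent error with a share above 50% and below 100%: 5 to 7 of 8 weekly kits, or 57 to 111 of 112 doses. On the whole-study reading, that conflict goes and a reverse one appears for a placebo participant given ALXN2050 throughout the PEP. The undefined *study period* is therefore part of the defect.

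The exposure is confined to by-group safety tables, including the two sets of adverse event and exposure summaries kept by the Addendum. It depends on such an error occurring. One participant is worth about 3.6 points in a 28-person arm or 7.1 points in the 14-person arm, for an event that participant had. These figures use planned arm sizes and rest on the dosing assumptions listed with the check. Because two stated rules cannot both be followed, this should be corrected, although it bears on no efficacy result.

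**What to change.** Use one rule in both places: actual treatment is the treatment taken for the majority of doses within the period being tabulated (the PEP, or the ALXN2050-treated period), with the planned arm kept if there is no majority.

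- In SAP Section 4, delete the one-dose parenthetical from both the Safety Set and the ALXN2050-Treated Set, and refer to 6.1.8.
- In 6.1.8, replace *study period* with the period analysed.
- Footnote any participant who received a wrong kit.
- Do not reassign individual events to another arm. That would put events in one arm's numerator while the participant stays in another's denominator.

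The cost is SAP wording, with no new data and no change to the efficacy analyses. It should be settled before the final tables are run.

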6.2. Appendix 2: Study and Participant Characteristics

6.2.1. Baseline Characteristics and Demographics

The following demographic variables will be summarized:

- Sex
- Race and ethnicity
- Age (years) at randomization: descriptive statistics (n, mean, SD, minimum, and maximum) and frequency of participants (< 65 and ≥ 65 years)
- Baseline weight: descriptive statistics (n, mean, SD, minimum, and maximum)
- Baseline weight: ≥ 40 and < 60, ≥ 60 and < 100, and ≥ 100 kg (n and percentage)Baseline height: descriptive statistics (n, mean, SD, minimum, and maximum)
- Baseline body mass index

The following disease characteristics will be summarized by descriptive statistics (n, mean, SD, minimum, and maximum) or by the number and percentage of participants in each category:MG-ADL total score at Baseline

- MG-ADL total score at Baseline ($< 7 \text{ versus} \ge 7$)
- QMG total score at Baseline Age (years) at MG diagnosisYears from MG diagnosis to informed consent
- Initial MG clinical presentation (ocular versus generalized)
- Time to gMG (if the initial clinical presentation was ocular MG): descriptive statistics (n, mean, SD, minimum, and maximum)
- Baseline MGFA clinical classification
- Maximum MGFA classification since diagnosis
- Ventilatory support since diagnosis (yes versus no)
- Experienced MG exacerbations or crisis (yes versus no)
- Type of MG event (exacerbation versus crisis)
- Any MG specific medications or therapies taken (yes versus no)

Summary statistics will be presented by treatment group and overall using the FAS and OLES. By-participant listings will be produced for all randomized participants.**Protocol Deviations**

All protocol deviations will be reviewed at the Blinded Data Review Meeting prior to the database lock. Any exclusion of participants from the PPS will be reviewed. Participants with the

following important protocol deviations (subset of all important protocol deviations) will be excluded from the PPS:

- Participants who did not meet inclusion criteria number 2, 3, 4 or 5
- Participants who violated exclusion criteria number 2, 3, 4, 19, 20, 21, 23 or 24.
- Participants who received any prohibited medication
- Participants who took a cholinesterase inhibitor within 8 hours prior to the QMG tests at Baseline and Week 8
- Participants who had changes in background MG medication in accordance with Section 6.5.1 of the protocol
- Participants who had unblinding of treatment allocation by the Investigator
- Participants who received incorrect randomized treatment

During Analysis 1 (Week 8), the number and percentage of participants with significant protocol deviations during the PEP will be summarized by treatment group and overall using the FAS. During Analysis 2 (Week 34), the number and percentage of participants with important protocol deviations during the PEP and ETP will be summarized by treatment group and overall using the ALXN2050-Treated Set. During the final analysis, the number and percentage of participants with important protocol deviations during the OLE Period will be summarized by treatment group and overall using the OLES. Protocol deviations from monitoring reports and other relevant sources will also be reviewed. All protocol deviations (important or not important) will be listed for all participants in the FAS.

6.2.3. Medical/Surgical History and Baseline Physical Examination

Medical history will be classified by SOC and PT using the latest available version of MedDRA and will be reported by treatment group and overall for the SS and OLES.

Baseline physical examination information will be summarized for the SS.

6.2.4. Prior/Concomitant Medication

Prior medications are defined as medications taken or received by participants prior to the first study treatment. Prior concomitant MG and non-MG medications will be summarized separately using the SS and OLES.

Concomitant medications are defined as medications taken or received by participants during the study after first study treatment. (Note: Some medications may be both prior and concomitant medications). During Analysis 1 (Week 8), concomitant MG and non-MG medications used in the PEP will be summarized separately using the SS. During Analysis 2 (Week 34), concomitant MG and non-MG medications used in the PEP or ETP will be summarized separately using the ALXN2050-Treated Set. During the final analysis, concomitant MG and non-MG medications used during the OLE Period will be summarized separately using the OLES.

Medications will be coded using the WHO DD (March 2021 or higher). Medication summaries by treatment group and overall using the number and percentage of participants will be presented

by WHO-DRUG Anatomical Therapeutic Chemical Level 4 class code and by WHO-DRUG generic name.

The number (percentage) of participants using prior nondrug therapies and procedures will be summarized by SOC and PT and will be reported by the treatment group for the SS. During Analysis 1 (Week 8), concomitant nondrug therapies and procedures performed in the PEP will be summarized by SOC and PT using the SS. During Analysis 2 (Week 34), concomitant nondrug therapies and procedures performed in the PEP or ETP will be summarized using the ALXN2050-Treated Set. During the final analysis, concomitant nondrug therapies and procedures performed during the OLE Period will be summarized separately using the OLES.

By-participant listings of prior and concomitant medications and nondrug therapies and procedures will be produced by treatment group using the SS.

6.3. Appendix 3: Additional Details on Statistical Methods

6.3.1. Clinical Deterioration

Clinical deterioration is defined as any of the following:

- Participants who experienced an MG crisis, which is defined as weakness from MG that is severe enough to necessitate intubation or to delay extubation following surgery. The respiratory failure is due to weakness of respiratory muscles. Severe bulbar (oropharyngeal) muscle weakness often accompanies the respiratory muscle weakness or may be the predominant feature in some participants; or
- Significant symptomatic worsening to a score of 3 or a 2-point worsening from Baseline on any one of the individual MG-ADL items other than double vision or eyelid droop; or
- Administration of rescue therapy to a participant whose, in the opinion of the Investigator or Investigator-designated physician, health would be in jeopardy if rescue therapy were not given (eg, emergent situations).

6.4. Appendix 4: Changes to Protocol-Planned Analyses

Not applicable in this version.

| Abbreviation | Definition | | |
|---------------------|---|--|--|
| AchR | acetylcholine receptor | | |
| AE | adverse event | | |
| AP | alternative pathway | | |
| Bb | completement factor Bb | | |
| bid | twice daily | | |
| BLQ | below the limit of quantification | | |
| C-SSRS | Columbia Suicide Severity Rating Scale | | |
| C3 | complement component 3 | | |
| CI | confidence interval | | |
| C _{max} | maximum observed concentration | | |
| СР | classical pathway | | |
| C _{trough} | concentration immediately prior to the administration of the next dose | | |
| CV | coefficient of variation | | |
| CV% | coefficient of variation percentage | | |
| ECG | electrocardiogram | | |
| eCRF | electronic case report form | | |
| EOS | end of study | | |
| ETP | Extended Treatment Period | | |
| FAS | full Analysis Set | | |
| FD | factor D | | |
| gMG | generalized myasthenia gravis | | |
| HIV | human immunodeficiency virus | | |
| ICF | informed consent form | | |
| IL-6 | interleukin 6 | | |
| LRP4 | low-density lipoprotein receptor-related protein 4 | | |
| LS | least-squares | | |
| MedDRA | Medical Dictionary for Regulatory Activities | | |
| MG | myasthenia gravis | | |
| MG-ADL | Myasthenia Gravis Activities of Daily Living | | |
| MGFA | Myasthenia Gravis Foundation of America | | |
| MGFA-PIS | Myasthenia Gravis Foundation of America Post-Intervention Status | | |
| MM | Myasthenia Gravis Foundation of America Post-Intervention Status minimal manifestation | | |
| MMP-10 | minimal manifestation matrix metalloproteinase 10 | | |
| MuSK | matrix incarioprocentase 10 muscle-specific tyrosine kinase | | |
| Neuro-QoL Fatigue | Quality of Life in Neurological Disorders Fatigue questionnaire | | |
| OLE | Open-label Extension | | |
| OLES | Open-label Extension Set | | |
| OR | odds ratio | | |
| PD | pharmacodynamic(s) | | |
| PEP | Primary Evaluation Period | | |
| PK | pharmacokinetic(s) | | |
| PPS | | | |
| PT | Per Protocol Set | | |
| QMG | Preferred Term Ouantitativa Muasthania Gravia | | |
| QRS | Quantitative Myasthenia Gravis | | |
| | combination of the Q wave, R wave, and S wave | | |
| QT | interval between the start of the Q wave and the end of the T wave in an ECG | | |
| QTc OTcF | corrected QT interval | | |
| QTcF | corrected QT interval using Fridericia's formula | | |
| SAP | statistical analysis plan | | |

1. STATISTICAL ANALYSIS PLAN ADDENDUM

Due to the lack of efficacy in ALXN2050 relative to Placebo based on the Week 8 interim analysis, Alexion decided to terminate Study ALXN2050-MG-201. There will be one final abbreviated CSR produced for the study including all applicable analyses.

The Statistical Analysis Plan (SAP) Addendum for final analysis details the changes from the planned analyses as described in the SAP Amendment Version 1.0 dated 27 Feb 2023 related to the analyses to be included in the final CSR. The original SAP was finalized on 23 Jun 2022. An SAP addendum was finalized on 20 Dec 2023 for Week 8 analysis.

1.1. Changes From Analyses Specified in the Protocol

See Section 1.2 for details.

1.2. Changes From Analyses Specified in the Previous Version of the SAP

- Primary endpoint: primary endpoint analyses will be performed as described in the SAP Amendment Version 1.0 Section 5.3.2. Sensitivity and supplementary analyses will not be performed.
- Secondary efficacy endpoints: only change from baseline in the QMG total score and change from baseline in the MG-ADL total score as described in the SAP Amendment Version 1.0 Section 5.4.1.1 and Section 5.4.1.3 (excluding the trend analysis to detect dose-response trend) will be performed. Descriptive summary of absolute and change from Primary Evaluation Period (PEP) baseline in MG-ADL and QMG total score will tabulate study visits through the entire study. Supplementary analyses will not be performed.
- PK/PD: PK parameter will not be reported as described in the SAP Amendment Version 1.0 Section 5.7.1.3. Population PK and exposure-response analysis will not be performed as described in the SAP Amendment Version 1.0 Section 5.7.3. All other PK/PD analyses will be performed.
- Biomarker: biomarker analysis will not be performed.
- Safety: All safety analyses will be performed as planned, as described in the SAP Amendment Version 1.0 Section 5.6 with all data collected until the end of study.
- No exploratory endpoint analyses will be performed.
- All other analyses (e.g., demographic, baseline disease characteristics, MG/non-MG medications/therapies, protocol deviation, etc), if not mentioned above, will be performed as planned.

Study exposure and adverse event data summaries will include the following two sets of analyses: (1) summary of the PEP data by Group 1, 2, 3; (2) summary of the ALXN2050 Treated Period data by Group 1, 2, 3a, 3b. Per-protocol Set and Re-randomized Set will be removed.

Medication summaries by treatment group and overall using the number and percentage of participants will be presented by WHO-DRUG Anatomical Therapeutic Chemical Level 3 class code and by WHO-DRUG generic name.

All planned listings other than the ones for exploratory biomarker endpoints will be produced.

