# **3. OBJECTIVES AND ENDPOINTS**

Objectives	Endpoints	
Primary		
To assess the efficacy of ALXN2050 compared with placebo in the treatment of gMG based on improvement in the MG-ADL total score	Proportion of participants with an MG-ADL total score reduction of $\geq 2$ points in any 4 consecutive weeks during the first 8 weeks and who did not receive rescue therapy	
Secondary		
To assess the efficacy of ALXN2050 compared with placebo in the treatment of gMG based on	• Change from baseline in QMG total score at Week 8	
improvement in the QMG total score	• Proportion of participants with at least a 3-, 4-, 5-, 6-, 7-, or 8-point improvement in the QMG total score at Week 8	
	• Proportion of participants with at least a 3-, 4-, 5-, 6-, 7-, or 8-point improvement in the QMG total score in any 4 consecutive weeks during the first 8 weeks and who did not receive rescue therapy	
To assess the efficacy of ALXN2050 compared with placebo in the treatment of gMG based on improvement in quality of life measures	
 
Change from baseline in Neuro-QoL™ Fatigue score at Week 8
 
	
To assess the efficacy of ALXN2050 compared with placebo in the treatment of gMG based on	• Change from baseline in MG-ADL total score at Week 8	
additional endpoints involving the MG-ADL total score	• Proportion of participants with at least a 3-, 4-, 5-, 6-, 7-, or 8-point improvement in the MG-ADL total score in any 4 consecutive weeks during the first 8 weeks and who did not receive rescue therapy	
	• Proportion of participants with at least a 2-, 3-, 4-, 5-, 6-, 7-, or 8-point improvement in the MG-ADL total score at Week 8	
PK/PD		
To characterize the PK/PD of ALXN2050 and to	Observed C max and C trough values over time	
establish the PK/PD relationship in participants with gMG	• Absolute values and change from baseline in plasma Bb concentration and serum AP activity over time	
Biomarker		
To assess the effect of FD inhibition on complement biomarkers	Plasma FD concentration, serum C3 concentration, and serum CP activity over time	

Objectives	Endpoints		
Safety			
To characterize the overall safety of ALXN2050 compared with placebo in participants with gMG	
 
Incidence of TEAEs and TESAEs over time
 
Changes from baseline in laboratory assessments
 
		
Tertiary/Exploratory			

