5.4. Secondary Endpoints Analyses

The secondary efficacy endpoint analysis will be performed on the FAS. Analyses for change from Baseline to Week 8 in the QMG total score, MG-ADL total score, and Neuro-QoL Fatigue score will be performed using both the FAS and PPS. Unless otherwise specified, baseline is defined as the last available assessment prior to the first dose of study intervention. The analysis results will be reported by treatment group for the PEP. For QMG, in the event that cholinesterase inhibitor was not withheld for at least 8 hours prior to administration of the QMG test on Day 1, the Screening Visit assessment will be used as Baseline. If cholinesterase inhibitor was not withheld for these visits (both Day 1 and Screening Visits), the Day 1 assessment will be used as baseline.

All secondary endpoint analyses will be performed at the first analysis (Week 8).

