5.4.1. Secondary Endpoints

5.4.1.1. Change From Baseline in the QMG Total Score at Week 8

The analysis will be performed on the FAS and PPS population.

A mixed-effects model with repeated measures (MMRM) will be used to estimate the treatment effect using all available data up to Week 8, irrespective of whether participants received rescue therapy. Missing data will not be imputed for the analysis.

The MMRM will include change from Baseline at each prespecified timepoint (Weeks 1, 2, 3, 4, 5, 6, 7, and 8) as the response variable; treatment group, study visit, and treatment-by-study visit

interaction as fixed categorical effects; and the baseline QMG total score as a covariate. The treatment effect will be evaluated via contrast for the treatment-by-visit term at Week 8. An unstructured covariance matrix will be used to model the correlations among repeated measurements within each participant. If a convergence issue occurs or the model performs poorly, alternative covariance matrix structures will be used in the following order until convergence or model performance issue is resolved: Toeplitz (TOEP), first order autoregressive (AR(1)), Compound symmetry (CS).

The Kenward-Rogers method will be used to estimate the denominator degrees of freedom.

The following statistics will be presented:

- Least-squares (LS) means per treatment group
- Standard error of LS means
- 90% CI
- LS mean difference (180 mg , 120 mg versus placebo, 180 mg versus 120 mg bid) and 90% CI of OR
- P-value for testing differences between treatment groups

Absolute levels and the change from Baseline in the QMG total score will be summarized in descriptive statistics by study visits and treatment groups.

A trend analysis to detect whether there is a decreasing (dose response) trend in the change from Baseline at Week 8 in the QMG total score will be presented, along with the p-value using the Jonckheere-Terpstra trend test.

5.4.1.2. Change From Baseline in the Neuro-QoL Fatigue Total Score at Week 8

The analysis method and missing data handling will be the same as described in Section 5.4.1.1. (with the baseline Neuro-QoL Fatigue total score as a covariate and change from Baseline to Week 4 and Week 8 as the response variable in the MMRM model)

5.4.1.3. Change From Baseline in the MG-ADL Total Score at Week 8

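### The SAP addendum keeps 2 of 7 secondary efficacy endpoints for the final report without endpoint-specific reasons, and the quality-of-life objective loses its only placebo-controlled result

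*SAP*

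**What the plan says.** Protocol Section 3 sets three secondary efficacy objectives.

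- **QMG** has three endpoints: the Week 8 change in score, a responder family worded "Proportion of participants with at least a 3-, 4-, 5-, 6-, 7-, or 8-point improvement in the QMG total score at Week 8", and the same thresholds for "improvement in the QMG total score in any 4 consecutive weeks during the first 8 weeks" without rescue.
- **Quality of life** is worded "To assess the efficacy of ALXN2050 compared with placebo in the treatment of gMG based on improvement in quality of life measures". Its one endpoint is the Week 8 change in Neuro-QoL Fatigue.
- **MG-ADL** has three endpoints: the Week 8 change and two responder families.

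SAP 5.4 schedules every secondary endpoint for Analysis 1 (Week 8). SAP 5.4.1.2, "Change From Baseline in the Neuro-QoL Fatigue Total Score at Week 8", specifies a repeated-measures model (MMRM) with the baseline score as covariate and the Week 4 and Week 8 changes as responses.

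The addendum opens by saying that the study is being terminated because the Week 8 analysis showed no efficacy relative to placebo. It continues: "There will be one final abbreviated CSR produced for the study including all applicable analyses". Its Section 1.2 then sets the scope: "Secondary efficacy endpoints: only change from baseline in the QMG total score and change from baseline in the MG-ADL total score", analysed as in SAP 5.4.1.1 and 5.4.1.3 but without the trend test. The primary analyses of SAP 5.3.2 are kept. So are by-visit descriptive summaries of both scales and all planned listings except those for exploratory biomarkers. Sensitivity, supplementary, exploratory and biomarker analyses are dropped. Addendum 1.1, on changes from the protocol, only points to 1.2.

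**The concern.** Termination explains a shorter report. It does not explain why these two secondary endpoints stay and the other five go. The dropped endpoints all concern the first 8 weeks, a period already analysed for the primary comparison. Ending the study later neither removes those data nor weakens the specified methods.

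At stake is completeness. The protocol gives participant-reported fatigue its own objective, and Table 7 justifies the instrument by the effect of fatigue on quality of life. A reader of the one final report would find no estimate, interval or comparison with placebo for it, and no reason for its absence.

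**Working it through.** The plan states no figure on this point, so the check is a count and a comparison of sections.

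**Step 1. Planned against kept.** Planned endpoints are from Protocol Section 3, methods from SAP 5.4.1, and retention from Addendum 1.2.

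| Objective | Endpoint | SAP section | In final report |
|---|---|---|---|
| QMG | Week 8 change | 5.4.1.1 | Yes |
| QMG | Week 8 responders | 5.4.1.4 | No |
| QMG | 4-consecutive-week responders | 5.4.1.6 | No |
| Quality of life | Neuro-QoL Fatigue, Week 8 change | 5.4.1.2 | No |
| MG-ADL | Week 8 change | 5.4.1.3 | Yes |
| MG-ADL | Week 8 responders | 5.4.1.5 | No |
| MG-ADL | 4-consecutive-week responders | 5.4.1.7 | No |

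Planned: 3 + 1 + 3 = 7. Kept: 2, and 2/7 = 29%. Dropped: 7 − 2 = 5, made up of one change score and four responder families.

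**Step 2. By objective.** QMG keeps 1 of 3, MG-ADL keeps 1 of 3, and quality of life keeps 0 of 1. One of the three secondary efficacy objectives is left without a comparison with placebo.

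**Step 3. Does the catch-all clause restore Neuro-QoL?** Addendum 1.2 says that analyses not mentioned go ahead as planned. The secondary-endpoint item is itself a mention and is limited by the word *only*, so the clause does not bring SAP 5.4.1.2 back. It arguably leaves SAP 5.9 standing, which includes a descriptive Neuro-QoL summary in the open-label extension. That summary has no placebo arm and cannot answer the objective.

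**Step 4. Are the data in hand?** Protocol Table 2 schedules Neuro-QoL at Day 1, Week 4 and Week 8, which are the time points the SAP 5.4.1.2 model uses. SAP Section 1 places Analysis 1 after the last randomized participant has completed or left the Primary Evaluation Period (PEP).

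**Step 5. What covers the dropped responder families?** They are cut-points of QMG and MG-ADL. Both scales keep their Week 8 MMRM and by-visit summaries, so the direction and average size of effect remain visible. The cover is not complete. The MMRM uses data regardless of rescue (SAP 5.4.1.1), whereas the 4-week families count rescue as non-response (SAP 5.4.1.6). For MG-ADL the retained primary endpoint still does this at 2 points. For QMG nothing retained does.

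**Step 6. Order in time.** The addendum cites the Week 8 lack of efficacy and measures its changes against SAP Amendment 1.0 of 27 Feb 2023. On the documents available, the reduction appears after the result. The addendum also mentions another one, finalized on 20 Dec 2023 for the Week 8 analysis, whose text is not included.

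**The case against.** A reader might infer that the sponsor saw the Week 8 data and then chose which outcomes to show. The documents do not support that.

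- The 20 Dec 2023 addendum governed the analysis at which all secondary endpoints were due. It may have shortened the list before the result was known, or the missing tables may already have been produced. Only the date order of the final addendum is established.
- The addendum declares lack of efficacy at the outset and keeps the whole of SAP 5.3.2, including the pairwise comparisons and the trend test. The cuts are listed openly and also reach sensitivity, supplementary, exploratory, biomarker and PK-parameter analyses. That fits a general abbreviation after termination.
- Protocol Section 9 says all results are to be read as exploratory, and 9.4.6.3 plans no multiplicity adjustment. No efficacy claim is inflated.

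A reader might also count every threshold: 1 + 6 + 6 + 1 + 1 + 6 + 7 = 28 planned quantities, with 2 kept. That overstates the loss. Of the 28, 25 (6 + 6 + 6 + 7) are nested cut-points of two scales whose continuous analyses remain, and SAP 5.4.1.4 to 5.4.1.7 planned intervals for them but no tests.

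Nor is the report necessarily the only public output, since Protocol 10.1.6 allows results to be posted on registries.

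These arguments limit the point to incomplete reporting. They do not supply the Neuro-QoL result. Listings, whose specifications SAP Section 1 places in a separate document, give individual values but no treatment comparison. Listing an omission openly does not give its reason.

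**Conclusion.** The point holds as one of incomplete, unexplained reporting. Five of seven protocol secondary efficacy endpoints are left out of the single final report. The substantive loss is one distinct instrument, Neuro-QoL Fatigue, and with it any placebo-controlled answer to the quality-of-life objective. The four responder families are a lesser loss because the QMG and MG-ADL change analyses stay. The primary analysis is not affected.

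This rests on two assumptions. First, the Week 8 interim analysis named in the addendum is taken to be the SAP's Analysis 1. SAP 5.8 plans no interim analysis, and the optional early look in Protocol 9.5 was to have no effect on the study's progress. Second, the final addendum is taken to be the operative statement of what the report contains. If the 20 Dec 2023 addendum already made these cuts before the result, or the tables already exist, the remedy shrinks to citing that decision or including the tables.

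**What to change.** In Addendum 1.2, extend the secondary-endpoint item as follows.

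1. Add the Neuro-QoL Fatigue MMRM of SAP 5.4.1.2 on the Full Analysis Set (FAS) for the PEP.
2. Report the responder tables of SAP 5.4.1.4 to 5.4.1.7 once, on the FAS.
3. For any secondary endpoint still omitted, state the reason, whether the omission was decided before or after the Week 8 result, and whether its Week 8 result had already been produced.

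The per-protocol and secondary trend analyses can stay out, since they are further looks at endpoints that would then be reported. No separate statement that the addendum followed the Week 8 comparison is needed, because its first sentence already says so.

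The cost is a few more tables in the abbreviated report, from data already collected and methods already written. If only one change is made, it should be item 1.
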